The overarching purpose of this study is to obtain preliminary evidence regarding the most efficacious frequency of *LLLT* treatments to obtain at least a 5% weight loss and to produce reduction in body circumference.

Hypothesis: We hypothesize that an increase frequency of *LLLT* treatments will produce a greater weight loss and greater reduction in body circumference when compared to a less frequent schedule of *LLLT*:

Group 1 weight loss > Group 2 weight loss > Group 3 weight loss

Group 1 reduction in body circumference > Group 2 reduction in body circumference > Group 3 reduction in body circumference

Aims, purpose, or objectives:

1. To compare the % of weight loss and reduction in body circumference at the end of 4 weeks for overweight individuals undergoing *LLLT* treatments at different frequencies

Study Design and Methods

Methods:

Study Design - This will be an open label clinical trial with all study participants receiving *LLLT*. We will obtain preliminary data on the efficacy of *LLLT* based on varying frequency of the *LLLT* treatments. We will focus this study on 60 overweight adults with a BMI of 25 to 29.9. We will assess changes in weight and waist circumference at end of treatment for group 1 (week 4) and group 2 (week 6) and group 3 (week 12). Participants will be randomized to receive *LLLT* treatments either 3 times a week for a duration of 4 weeks (group 1); 2 times a week for a duration of 6 weeks (group 2); or once a week for a duration of 12 weeks (group 3).

Study Procedures: We will use standardized procedures to ensure that uniform instructions are provided to all participants and that recruitment and screening result in the enrollment of appropriate study participants. All Study Case Report Forms are paper documents and also function as study source documents. The data will be entered into an online electronic data program (Redcap) by research staff within 7 days of the completed study visit. Study participant data on this system will be identified using unique subject IDs, not personal identifiers. This data entry system will provide immediate feedback on the majority of data integrity issues, including implausible entries, and checks of consistency between variables.

Study Processes and Procedures

Intervention

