LLLT treatments. Everyone will be in the study for 6 months, but will be in treatment for varying periods of time based on the randomization group they will be assigned:

1. 12 treatments of LLLT 3 times per week (M W F) for a duration of 4 weeks
2. 12 treatments of LLLT 2 times per week (T Th) for a duration of 6 weeks
3. 12 treatments of LLLT 1 time per week for a duration of 12 weeks

Inclusion Criteria: Potentially eligible subjects must:

1. be over 18 years of age;
2. have a body weight of greater than 50 kg (110 pounds);
3. have a BMI 25–29.9 kg/m²;
4. be able to participate fully in all aspects of the study; and
5. have understood and signed study informed consent.

Exclusion Criteria: Subjects will be excluded if they:

1. have used weight loss medications or participated in a weight loss program within the past 30 days;
2. are currently taking supplements known to affect weight, such as *garcinia cambogia*;
3. have had weight fluctuations of 20 pounds or more in the past 6 months (self-report);
4. have an implanted device (including pacemaker or lap band) in the targeted area of LLLT;
5. have a known active eating disorder;
6. have a known, active, untreated clinically significant psychiatric condition (alcohol or substance abuse, psychosis, bipolar disorder, or depression);
7. have used an investigational drug within 30 days of study enrollment;
8. are currently pregnant or lactating, or are of child-bearing potential or are likely to become pregnant during the medication phase and are unwilling to use a reliable form of contraception; Acceptable forms include:
 - a. Hormonal methods, such as birth control pills, patches, injections, vaginal ring, or implants
 - b. Barrier methods (such as a condom or diaphragm) used with a spermicide (a foam, cream, or gel that kills sperm)
 - c. Intrauterine device (IUD)
 - d. Total hysterectomy or tubal ligation
 - e. Abstinence (no sex)
9. have a history of any major cardiovascular events including heart valve disease, cardiac arrhythmias, congestive heart failure, acute coronary syndrome, stroke, transient ischemic attack, or peripheral vascular disease;
10. have current uncontrolled hypertension (systolic > 160 mm Hg or diastolic > 95 mm Hg) documented on 2 separate occasions;

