The purpose of a phase II trial is to decide whether additional studies of the experimental regimen are warranted and to provide preliminary data for designing a larger phase III trial to confirm efficacy. Although there has been debate about the value of formal statistical comparisons in phase II trials, we agree with those who propose that formal comparisons are appropriate under the caveat that phase II studies are not expected to provide reliable definitive comparisons using a traditional two-sided type I error rate of 0.05.(references). For a randomized phase II trial, a one-sided test with a false-positive (type I error) rate of 0.20 is considered appropriate for the primary comparison to assess whether additional studies of the given regimen are warranted.

For the current study the primary endpoint is change in waist circumference (WC) from baseline. For the primary analysis, the change in WC from baseline to week 4 will be compared across frequency groups.

Data Analysis Plan:

Data related to subject recruitment will be summarized, including the frequency of calls and the reasons for failing screening criteria.

Baseline characteristics and treatment compliance of the enrolled participants will be presented overall and also separately for each of the treatment groups. In all cases, data will be summarized using mean \pm SD for continuous variables and frequency percentages for nominal variables. Treatment adherence will be quantified for each individual by calculating the percentage of treatment sessions attended and the percentage of medication used. The percentage of subjects who discontinue study participation and the reasons for discontinuing study participation will be summarized. Changes in measures of central adiposity and weight from baseline will be summarized at each study visit. The primary outcome of interest is change in waist circumference from baseline to week 4. For the primary comparison, the group receiving one LLLT session per

week will be the control group and the groups receiving two and three sessions per week will be considered the experimental groups. The mean change from baseline WC for each of the experimental groups will be compared to control using the two-sample t-test. For these comparisons, a one-tailed p-value of 0.20 or less will be considered evidence suggesting that studies utilizing increased frequency of LLLT sessions are warranted.

Sample-size justification:

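### The week-4 tests answer Aim 1, but no between-group difference is planned at equal session counts, so a larger final waist reduction cannot be told from the same reduction reached sooner

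*Combined protocol and SAP*

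**What the plan says.** The purpose of the study is to "obtain preliminary evidence regarding the most efficacious frequency of" laser treatment, and the hypothesis orders the three groups by frequency. Aim 1 sets a fixed date: it compares percentage weight loss and "reduction in body circumference at the end of 4 weeks for overweight individuals undergoing" the different schedules.

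All groups are assigned the same number of sessions over different periods. Under Subject Information, group 1 has "12 treatments of LLLT 3 times per week (M W F) for a duration of 4 weeks" and group 3 has "12 treatments of LLLT 1 time per week for a duration of 12 weeks"; group 2 has 12 sessions at two per week over 6 weeks.

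The Data Analysis Plan follows Aim 1: "The primary outcome of interest is change in waist circumference from baseline to week 4". Each more frequent group is compared with the once-weekly group by a two-sample t-test. A one-tailed p-value of 0.20 or less counts as a signal that studies of more frequent sessions are worth doing.

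The Study Design paragraph also plans assessment of "waist circumference at end of treatment for group 1 (week 4) and group 2 (week 6) and group 3 (week 12"). The Data Analysis Plan provides only for summaries of change at each visit. Neither it nor the Sample-size justification names a between-group difference at end of treatment.

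**The concern.** The study asks about frequency, but at the one time point where groups are compared the schedules differ in how much of the course has been given. A positive week-4 result fits two accounts. Under the first, more frequent sessions produce a larger reduction once the course is complete. Under the second, all schedules end at the same reduction and the more frequent ones get there earlier. These point to different next studies.

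That matters because Statistical Considerations says a phase II trial should "provide preliminary data for designing a larger phase III trial to confirm efficacy". The equal-session assessment that bears on the choice is already planned, but no estimate is drawn from it, and the plan does not say that the week-4 result leaves the question open.

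**Working it through.** **Inputs.** Schedules of 3 per week for 4 weeks, 2 per week for 6 weeks and 1 per week for 12 weeks (Subject Information). From the Sample-size justification: 20 per group, SD 1.9 cm, target difference 1.0 cm, one-tailed alpha 0.20, and a mean change of −1.1 cm in earlier once-weekly participants. That section does not say how many weeks or sessions lie behind the −1.1 cm.

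**Step 1: the plan's own power.** SE of a difference = 1.9 × √(2/20) = 0.601 cm, with 38 degrees of freedom. From the noncentral t distribution, one-sided 0.20, power at 1.0 cm is 79.2%. The stated figure of about 80% is reproduced and is not in dispute.

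**Step 2: scheduled sessions.**

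| Group | By week 4 | By end of treatment |
|---|---|---|
| 1 (3 per week) | 3 × 4 = 12 | 3 × 4 = 12 (week 4) |
| 2 (2 per week) | 2 × 4 = 8 | 2 × 6 = 12 (week 6) |
| 3 (1 per week, control) | 1 × 4 = 4 | 1 × 12 = 12 (week 12) |

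At week 4 the experimental groups are ahead of control by 12 − 4 = 8 sessions (8/12 = 67% of the course) and 8 − 4 = 4 sessions (4/12 = 33%). At end of treatment the lead is zero. These counts are scheduled sessions; attendance may differ.

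**Step 3: precision of an end-of-treatment difference.** If the SD of 1.9 cm also holds at later visits and all 20 per group are measured, the 95% CI half-width is 2.024 × 0.601 = 1.22 cm.

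**Step 4: illustration only.** Suppose each session adds the same lasting reduction and the schedules do not differ once 12 sessions are complete. The expected week-4 difference is then the lead in sessions times the effect per session. The probability of a positive signal (one-tailed p ≤ 0.20) comes from the noncentral t distribution with noncentrality difference/0.601.

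| Reading of the 1.1 cm reduction | Per session | Week-4 difference, 3 vs 1 and 2 vs 1 per week | P(signal) |
|---|---|---|---|
| Sessions have no effect | 0 | 0 and 0 cm | 20% and 20% |
| All due to 12 sessions | 1.1/12 = 0.092 cm | 8 × 0.092 = 0.73 and 4 × 0.092 = 0.37 cm | 64.5% and 40.7% |
| All due to 4 sessions | 1.1/4 = 0.275 cm | 8 × 0.275 = 2.2 and 4 × 0.275 = 1.1 cm | 99.7% and 83.7% |

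In every row the true difference at 12 sessions each is zero. The table shows that a week-4 signal can arise without an end-of-course difference. It does not show how likely that is in this trial.

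**The case against.** The strongest reply is that nothing planned is wrong. Aim 1 asks about 4 weeks, the primary analysis matches it, and the decision rule claims only that further studies are warranted. All of this stands. A reader might infer that the week-4 comparison is invalid, confounded or set at the wrong time. The documents do not support that: it is a randomised comparison of schedules at a date that the aim itself names.

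A second reply is that, with the total fixed at 12 sessions, higher frequency and faster delivery are the same manipulated variable, so no analysis could separate them. This is right. The question left open is narrower: effect by week 4 against effect over the completed course.

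Third, the planned summaries at each visit, if given by group with numbers, means and SDs, would let anyone compute the missing difference. That is largely true, and it keeps the point small. What it does not supply is a comparison chosen in advance or a statement of what week 4 leaves open.

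Fourth, the end-of-treatment difference has its own imbalance, because it falls at weeks 4, 6 and 12. It equalises scheduled sessions but not elapsed time, whereas week 4 does the reverse. If waist circumference drifted by, say, 0.5 cm in the once-weekly group for other reasons, the estimate would move by 0.5 cm, half the target. It can inform the next study but cannot isolate frequency.

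**Conclusion.** The point holds as a minor, inexpensive improvement. The only planned between-group tests fall when 12, 8 and 4 sessions are scheduled. A planned assessment at 12 scheduled sessions each has no between-group estimate attached, and the limit on reading a positive week-4 result is not stated. The session counts follow from the schedules alone. The ±1.2 cm precision rests on the SD of 1.9 cm holding at later visits with 20 measured per group.

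A reader might take the 41% to 99.7% figures as false-positive rates of the trial. They are not. They depend on a linear, lasting effect per session and on an undated −1.1 cm, and where sessions work the week-4 difference they detect is real. Nor would agreement between the week-4 and end-of-treatment estimates be separate confirmation. Group 1's week-4 value enters both 3-per-week contrasts, and repeated measurements on the same people link the two 2-per-week contrasts.

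**What to change.** Keep week 4 as primary, with its decision rule and sample size unchanged. Add to the Data Analysis Plan:

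> A positive week-4 result suggests greater waist circumference reduction by week 4 with more sessions scheduled (12 or 8 vs 4); it does not by itself indicate an advantage of frequency over a completed 12-session course. As a supportive, estimation-only analysis outside the decision rule, the difference in waist circumference change from baseline to end of treatment (12 scheduled sessions; weeks 4, 6 and 12) between each experimental group and the once-weekly group will be reported with a 95% CI, alongside the sessions actually attended.

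The word *suggests* is deliberate, since each test has a 20% one-sided error rate.

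The protocol says "Everyone will be in the study for 6 months", so if waist circumference is already measured at week 12 in all groups, report that difference in the same way. It equalises calendar time, but the scheduled courses will have ended about 12 − 4 = 8, 12 − 6 = 6 and 0 weeks earlier.

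State these limits beside the estimates: unequal calendar time at end of treatment, unequal time since the last session at week 12, a CI wider than the 1.0 cm target, and no independence from the week-4 result. Attach no agreement rule. The cost is two sentences and two reported differences (four with week 12). No new visit, test or participant is needed.

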The primary endpoint for the current investigation is change in WC from baseline to week 4. The group having one LLLT session per week will be considered the control group. From our previous study, the mean \pm SD change in WC from baseline in those receiving 1 LLLT session per week was -1.1 ± 1.9 cm. In order to be considered meaningful, we would expect an increased frequency of LLLT sessions to result an additional reduction of approximately 1.0 cm. Under the assumption that the SD is 1.9cm, a sample-size of N=20 per group will provided statistical power (one-tailed, alpha=0.20) of approximately 80% to conclude that additional studies are warranted (i.e. detect a difference between groups of 1.0 cm). Therefore, a sample-size of N=20 per groups will be used for the present study.

References

2. Erchonia Corporation. Zerona. [Web Page]. 2011; <http://www.myzerona.com/professional>. Accessed 01 Sept 2011.

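### Optional, low-cost improvement (not an error): a prespecified ANCOVA on baseline waist circumference would hold each comparison's 20% false-signal rate conditional on whatever chance baseline imbalance arises

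*Combined protocol and SAP*

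**What the plan says.** The Data Analysis Plan states that "The primary outcome of interest is change in waist circumference from baseline to week 4", and the Sample-size justification repeats this endpoint. The once-weekly group is the control, and "the groups receiving two and three sessions per week will be considered the experimental groups". The mean change in each of those two groups "will be compared to control using the two-sample t-test". On the decision rule, "a one-tailed p-value of 0.20 or less will be considered evidence suggesting that studies utilizing increased frequency of LLLT sessions are warranted".

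The test uses baseline WC only through subtraction. Its other planned use is descriptive: "Baseline characteristics and treatment compliance of the enrolled participants will be presented overall" and by group. No covariate adjustment is planned. The Study Design section says "Participants will be randomized to receive" one of the three schedules and mentions no stratification. The Sample-size justification says that "a sample-size of N=20 per group will provided statistical power (one-tailed, alpha=0.20) of approximately 80" per cent for a 1.0 cm difference with an SD of 1.9 cm.

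**The concern.** A change score removes the effect of baseline fully only if change is uncorrelated with baseline. If people with larger waists tend to lose more, a group that happens to start larger will show more reduction with no schedule effect at all. Over all possible randomisations this averages out, so the t-test keeps its nominal 20%. In the one randomisation that is carried out it does not average out, and the chance of a false signal then lies above or below 20% according to which group started larger.

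The signal threshold is low: an observed difference of about 0.51 cm is enough. Groups are small and no stratification on WC is described. If the baseline table showed a visible imbalance, an adjustment chosen at that point would be unplanned and open to challenge. Deciding beforehand avoids this.

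**Working it through.** **Inputs from the documents.** 20 per group; SD of change 1.9 cm; difference 1.0 cm; one-sided alpha 0.20 for each comparison (Sample-size justification and Data Analysis Plan).

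**Assumptions not in the documents.** Equal WC variance at baseline and week 4; baseline WC SD of 5 to 12 cm; normal data with a linear common slope and common residual variance.

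**1. The plan's own figure.** SE of the difference = 1.9 × √(2/20) = 0.601 cm. With 38 df the one-sided 0.20 critical value is 0.851, so the critical difference is 0.851 × 0.601 = 0.511 cm. Power at 1.0 cm from the noncentral t distribution is 79.2%. The stated figure of about 80% reproduces.

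**2. Correlation of change with baseline.** With equal variances, the correlation is negative with size |r| = (SD of change) / (2 × baseline SD) = 1.9 / (2 × SD). This gives 0.190, 0.136, 0.095 and 0.079 for SDs of 5, 7, 10 and 12 cm.

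**3. How often imbalance arises.** For a given pair of groups the standardised baseline difference is standard normal. It exceeds one SE in either direction with probability 2 × (1 − Φ(1)) = about 32%. One SE is SD × √(2/20), or 1.6 cm at SD 5 and 3.8 cm at SD 12. It shifts the observed difference in change by |r| × 0.601, or 0.11 cm at SD 5 and 0.05 cm at SD 12. That shift is part of the 0.60 cm SE, not additional error.

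**4. False-signal rate given the imbalance.** With no true effect and an imbalance of k SE, the t-test's rate is P(T > 0.851/√(1 − r²)), where T is noncentral t with 38 df and noncentrality k|r|/√(1 − r²). Positive k means the imbalance favours the more frequent group; with a negative correlation, that group starts with the larger waist.

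| Assumed baseline SD (cm) | Abs. r | t-test rate, k = +1 | t-test rate, k = −1 | ANCOVA rate |
|---|---|---|---|---|
| 5 | 0.190 | 25.3% | 14.7% | 20% |
| 7 | 0.136 | 23.8% | 16.2% | 20% |
| 10 | 0.095 | 22.6% | 17.4% | 20% |
| 12 | 0.079 | 22.2% | 17.8% | 20% |

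At k = ±2 the same formula gives 31.8% / 10.7% at SD 5 and 24.6% / 15.8% at SD 12. Simulation with the imbalance fixed at +1 / −1 SE (200,000 trials each) gave 25.3% / 14.6% for the t-test and 20.0% / 19.9% for ANCOVA at |r| = 0.19. At |r| = 0.079 it gave 22.2% / 17.7% and 20.0% / 19.9%.

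**5. Power of the replacement.** For one ANCOVA on all three groups (56 df), the variance of a contrast averaged over imbalance is 1.9² × (1 − r²) × (2/20) × (1 + 1/55). At SD 5 this is 3.61 × 0.9639 × 0.1 × 1.0182 = 0.354, so the SE is 0.595 cm. Power for 1.0 cm is 79.8%, 79.3%, 79.1% and 79.0% at SDs of 5, 7, 10 and 12 cm, against 79.2% for the t-test. The changes are +0.5, +0.1, −0.1 and −0.2 point. Break-even is at |r| of about 0.12 (SD about 7.9 cm). At r = 0 power is 78.9%, a loss of about 0.35 point.

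**6. What stays the same.** With no true effect in either group, the two comparisons share a control and have correlation 0.5. The chance of at least one false signal is about 31% by the bivariate normal. Simulation gave 31.1% for both methods at |r| = 0.19 and 31.3% for both at |r| = 0.079.

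**The case against.** The strongest reply is that nothing is broken. The planned test is valid, fully specified and powered as stated. The protocol's 20% is an unconditional rate, which the t-test meets; asking for 20% given the imbalance is an added criterion. The Statistical Considerations section also says that a phase II comparison is not meant to be definitive, so a rate of 22% to 25% or 15% to 18% is unlikely to alter how the rule is used. About 68% of randomisations have less than one SE of imbalance. Averaging the formula in step 4 over the imbalance distribution gives a mean absolute departure from 20% of 4.2, 3.0, 2.1 and 1.8 points at SDs of 5, 7, 10 and 12 cm. The size of the benefit rests on figures the documents do not contain.

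The power comparison can also be challenged, because part of what the ANCOVA gains comes from pooling the variance over three groups. Against an unadjusted contrast with the same pooling (57 df, power 79.3%), adjustment changes power by +0.4, 0.0, −0.2 and −0.3 point. Finally, ANCOVA adds assumptions of linearity and a common slope, and uses the third group's variance.

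All of this is correct, and it limits the point to an optional improvement. It does not remove it. The case does not rest on power, and dependence on chance imbalance can be eliminated with a measurement the trial already takes. Some correlation should be expected, since equal variances before and after treatment make it negative by construction.

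**Conclusion.** The point holds as something to consider, not as a defect. The t-tests keep 20% per comparison on average. Conditional on a one-SE baseline WC imbalance, the rate is between 22.2% and 25.3% or between 14.7% and 17.8%, according to direction, for an assumed baseline SD of 5 to 12 cm with equal variances. ANCOVA keeps it at 20% under a linear common slope and common residual variance. A larger |r|, and so a larger effect, is possible only if the equal-variance or SD assumption fails; if r is zero there is no benefit. No imbalance is reported in the documents: the point concerns whatever chance imbalance arises. ANCOVA on baseline WC does not deal with imbalance in other factors or with the roughly 31% chance of at least one false signal. Confidence is medium, because r and the baseline SD are unknown.

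**What to change.** Prespecify as the primary analysis one ANCOVA of week-4 WC change on group (three levels) and baseline WC. Test three sessions against one and two sessions against one as contrasts from that model, each at the same one-sided 0.20. Keep the planned t-tests as sensitivity analyses, and state before any data are seen that the ANCOVA decides if the two disagree.

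This takes one or two sentences in the Data Analysis Plan. It needs no new data and no additional participants, because baseline WC is already required for the endpoint. The price is the small power change in step 5, at worst about 0.35 point, and the added slope and variance assumptions.
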